2.2 BACKGROUND

CLINICAL SIGNIFICANCE

The public health burden of out-of-hospital cardiac arrest (OHCA) is enormous, with approximately 395,000 cases and more than 350,000 deaths each year in the United States.^{1,2} Survival rates vary widely by area and population.³ However, despite improvements in recent years, overall survival to hospital discharge for OHCA remains under 12% even in the best EMS systems.^{2,6} Presenting rhythm is a predictor of survival after OHCA.⁸ Numerous studies show higher rates of survival to hospital discharge in patients with an initial shockable rhythm (ventricular fibrillation or pulseless ventricular tachycardia [VF/VT]) (21-35%) compared with patients with nonshockable rhythms (1-8%).²⁻⁹ Although only 20-35%

of EMS-treated patients with OHCA have VF/VT,^{2-6, 20-22} and the incidence of VF/VT among patients with cardiac arrest has decreased in recent years,²³ these patients still make up 70-80% of all cardiac arrest survivors with favorable neurological function (modified Rankin Scale score [mRS] ≤3).^{4, 24, 25} Nevertheless, more than 50% of patients with VF/VT OHCA are refractory to current treatment and never achieve return of spontaneous circulation (ROSC) or die before they are admitted to the hospital.² A large number of patients with VF/VT OHCA have acute or chronic coronary artery disease (CAD).^{11, 19} The incidence of clinically significant coronary stenosis is greater than 60% in patients resuscitated from VF/VT cardiac arrest^{13-15, 26-30} and even higher—70-84%—in patients with refractory VF/VT cardiac arrest.^{4, 10-19} We believe that it is the burden of significant CAD that limits the ability of conventional CPR to allow for successful resuscitation. (Figure 1) *This observation is a critical insight. Without addressing the root cause and mitigating coronary ischemia with revascularization, conventional CPR efforts alone can offer little advantage, as currently low survival rates suggest.*

[figure not shown]

Figure 1. The breakdown of shockable rhythms based on the presence or absence of return of spontaneous return of circulation and the presence or absence of ST elevation on the 12-lead ECG. Corresponding % of coronary artery disease (>70% stenosis) and acute (thrombotic) lesions are presented. VF/pVT: Ventricular fibrillation/pulseless ventricular tachycardia; ROSC: return of spontaneous circulation. **[name] et al.** The Evolving Role of the Cardiac Catheterization Laboratory in the Management of Out-of-Hospital Cardiac Arrest Patients: **A Scientific Statement from the American Heart Association.** Circulation 2019. In press.

Coronary stenosis or occlusion can be potentially reversed by advanced perfusion/reperfusion strategies.^{11, 12, 19} Thus, the underlying cause of cardiac arrest is likely to be reversible in most patients with refractory VF/VT OHCA. However, these patients currently have a poor prognosis because they require early identification of the potentially reversible coronary cause in order to have any significant chance to be resuscitated, but they are too unstable to be considered for coronary angiography and PCI by most cardiology practices. Therefore, ROSC is generally required before the patient can gain access to the cardiac catheterization laboratory (CCL).³¹⁻³³ This can potentially be addressed by early initiation of extracorporeal CPR (ECPR), a method of extracorporeal life support (ECLS) using a device for

extracorporeal membrane oxygenation (ECMO). ECMO can expedite circulatory support, alleviate the ischemic burden of prolonged resuscitation, ameliorate metabolic degradation and—most importantly—provide the hemodynamic stability needed to expand the opportunity for CCL-based diagnostic and therapeutic interventions.³⁴

The treatment strategy for patients with refractory VF/VT cardiac arrest should clearly include achievement of adequate coronary and cerebral perfusion by using mechanical CPR devices, optimizing hemodynamics, facilitating early transport, and providing ongoing treatment during transport. Compared with a strategy that provides these measures but requires ROSC before the patient can gain access to the CCL, the addition of early circulatory support by expediting ECMO initiation, can be used as the stabilization platform to facilitate PCI when clinically indicate. That approach is expected to significantly improve survival to hospital discharge and functionally favorable survival by 3-6 months post hospital discharge. However, emergent ECMO initiation at short notice with field activation carries significant human and infrastructural costs in addition to the technical, procedural, and management challenges that arise after the patient is hospitalized. Therefore, before major infrastructural investments can be made, both the contribution of **early ECMO facilitated resuscitation** to the management and survival of this population and the relative cost of such a strategy need to be assessed in a randomized clinical trial.

SUPPORTING SCIENCE – ANIMAL STUDIES:

IMPORTANCE OF CORONARY REVASCULARIZATION IN PORCINE MODEL OF REFRACTORY ISCHEMIC VF.

Our group developed a pig model in which occlusion of the left anterior descending (LAD) coronary artery was induced via balloon inflation.³⁵ After 5 min, VF was induced by delivering intracardiac current and left untreated for 8 min. CPR was performed for 3 min, and advanced cardiac life support (ACLS) was performed until ROSC was achieved or the pig had received 15 min of CPR. Of 27 pigs, 21 had ROSC within 15 min; 6 pigs did not have ROSC within 15 min and were classified as having refractory VF. If ROSC was not achieved in these pigs within 45 min of continued ACLS, reperfusion was attempted via LAD balloon deflation and removal with continued CPR until ROSC or another 10 min of resuscitation. **Results:** *ROSC was achieved in 4 of 6 animals, but only after reperfusion.* **Conclusions:** *In animals with refractory VF, reperfusion was necessary to achieve ROSC.* **Relevance:** In refractory ischemic VF arrest that does not respond to standard ACLS, coronary revascularization/reperfusion appears to be necessary for ROSC. Because patients with refractory VF have a very high rate of acute and chronic CAD, PCI may be their only option for successful resuscitation.

ECMO-FACILITATED PCI AND SHORT-TERM SURVIVAL IN A PORCINE ISCHEMIC LAD MODEL OF REFRACTORY VF ARREST.

Our team reported the results of ischemic refractory VF in 33 intubated and anesthetized female pigs (44±3 kg).³⁴ VF was induced by endovascular balloon occlusion of the ostial LAD. After 5 min of untreated VF and 10 min of CPR, pigs were randomized to LAD reperfusion at min 45 with ongoing CPR without ECMO (16 pigs) vs venoarterial ECMO cannulation at minute 45 of CPR (17 pigs) and subsequent

LAD reperfusion. Resuscitation continued until ROSC was achieved or 60 min of CPR had elapsed. Animals without ROSC at 60 min were declared dead. Resuscitated animals were maintained for 4 hours. The primary endpoint was 4-h survival. **Results:** 4-h survival was significantly improved in pigs with ECMO (82%) compared to those without ECMO (31%), $p=0.003$. After 4h, 9 pigs with ECMO were suitable for decannulation. **Conclusions:** ECMO-facilitated coronary reperfusion significantly improved 4-hour survival compared with reperfusion facilitated by CPR alone. ECMO support enabled cardiac recovery and hemodynamic stability within 4 hours. **Relevance:** These results support the idea that, although coronary reperfusion is a necessary condition for achieving ROSC, *after prolonged (45 min) CPR the metabolic ischemic substrate requires circulatory support to improve outcomes.*

SUPPORTING SCIENCE – HUMAN CLINICAL STUDIES (TABLE 1)

Table 1. Survival in patients with refractory OHCA treated with advanced perfusion techniques (ECMO and PCI)

	Enrollment years	ECMO cannulation	Number of patients		Survival rates		
			OHCA n	VF/VT n (%)	All OHCA n (%)	CPC 1-2 n (%)	VF/VT n (%)
Kagawa et al 2012	7.5	ED	42	23 (55)	7 (17) ^a	6 (14) ^a	17/46 (37) ^c
Avali et al 2012	5	ED/CIU/CCL	18	16 (89)	1 (5.5) ^a	1 (5.5) ^a	-
Haneva et al 2012	5	ED	26	12 (46.2)	4 (15) ^b	27/85 (32) ^c	-
Leick et al 2013	2	CCL	28	8 (28.6)	11 (39) ^a	8 (28.5) ^a	-
Maekawa et al 2013	4.5	ED	53	32 (60.4)	17 (32.1) ^b	8 (15.1) ^b	-
Wang et al 2014	5.5	ED	31	15 (48.4)	12 (38.7) ^b	8 (25.8) ^b	-
Johnson et al 2014	7	ED	15	11/26 (42) ^a	1 (6.6) ^b	3/26 (11.5) ^{bc}	-
Sakamoto et al 2014	3	ED	234	234 (100)	68 (29) ^{ad}	32 (13.7) ^{ad}	68 (29) ^{ad}
Kim et al 2014	7.5	ED	55	31 (56.4)	9 (16.4) ^b	8 (14.5) ^b	-
Stub et al 2015	3	ED	11	11 (100)	5 (45) ^b	5 (45) ^b	5 (45) ^b
Pozzi et al 2016	4	ED	68	19 (28)	6 (8.8) ^b	3 (15.8) ^b	6 (31.5) ^b
Lee et al 2016	4	ED	23	20 (87)	10 (43.5) ^a	7 (30.4) ^a	8 (40) ^a
Fjølner et al 2017	3.5	CCL	21	9 (43)	7 (33) ^b	7 (33) ^b	5 (55.6) ^b
Lambaut et al 2017	4	Field vs ED	156	81 (58) ^e	21 (13.5) ^b	21 (13.5) ^b	21 (25.9) ^b
Schober et al 2017	10	ED	7	4/7 (57)	1 (14) ^f	-	-
[name] et al 2017	1	CCL	62	62 (100)	28 (45) ^b	26 (42) ^b	28 (45) ^b

ECMO = extracorporeal membrane oxygenation; OHCA = out-of-hospital cardiac arrest; PCI = percutaneous coronary intervention. ^a30-day survival. ^bSurvival to hospital discharge. ^cPercentage includes OHCA + IHCA. ^dThis is per protocol analysis. Intention-treat-analysis was 32/260 (12.3%). ^e139 patients with available data. ^f6-month survival.

According to the 2016 Extracorporeal Life Support Organization (ELSO), survival to discharge following ECPR for cardiac arrest that is refractory to conventional CPR was 29% in their registry database of 2885 adults.³⁶ Published studies have reported widely varying results. Most of the experience is from non-US cohorts, mainly in Asia.^{16, 17, 25, 37-39}

Several studies of patients unresponsive to CPR who received ECMO (and PCI when indicated) found worse outcomes with OHCA vs in-hospital cardiac arrest (IHCA). [Kagawa et al](#)³⁷ analyzed data for 86 patients with OHCA or IHCA unresponsive to CPR who received ECMO (and PCI when indicated). Survival to day 30 was 29% overall, 17% (7/42) for OHCA vs 41% (18/44) for IHCA, and 37% (17/46) for patients presenting with VF/VT vs 20% (8/40) for patients with non-shockable rhythms. Compared with patients who did not survive to day 30, survivors had a significantly shorter time interval from collapse to initiation of ECMO (54 minutes [34–74 minutes] vs 40 [25–51] minutes, $p=0.002$) and a higher rate of intra-arrest PCI (70% vs 88%; $p=0.04$). [Wang et al](#)¹⁶ retrospectively described a cohort of 230 patients who had received ECPR during a period of 5 years (31 patients with OHCA and 199 with IHCA). No

significant differences were observed between OHCA and IHCA in rate of survival to discharge (38.7% vs 31.2%, $p>0.05$) or functionally favorable outcome (25.8% vs 25.1%, $p>0.05$). Duration of ischemia (collapse to ECPR) was a key issue for survival. The authors attributed the high survival rate in patients with OHCA compared to previous studies^{37, 38, 40, 41} to a well-organized and rapid-response EMT system, efficiency in handling patient transportation and resuscitation, and an equipped cart in the emergency room rather than in the ICU, shortening the duration of ischemia. In Australia, Stub et al¹⁰ treated 26 patients with refractory prolonged cardiac arrest with the CHEER protocol (mechanical CPR, Hypothermia, ECMO and Early Reperfusion) during a period of 32 months. Of 15 patients with IHCA, all had ROSC with ECMO, and 9 (60%) survived. In 11 patients with OHCA (all with VF), ROSC was achieved in 2 patients before ECMO was initiated and in 8 of 9 patients placed on ECMO. A total of 5 OHCA patients (45%) survived, including 3 of 9 patients who were placed on ECMO. Avali et al⁴⁰ reported their experience with ECMO support in patients with refractory cardiac arrest (IHCA, $n=24$; OHCA, $n=18$). Survival to discharge from intensive care was 46% (11/24) for IHCA and 5% (1/18) for OHCA ($p<0.05$). At 6 months, survival rates with good neurological outcome were 38% (9/24) for IHCA and 5% (1/18). Haneya et al⁴¹ analyzed a total of 85 consecutive adult patients treated with ECLS. Thirty-day survival was 42% (25/59) in patients with IHCA and 15% (4/26) in patients with OHCA ($p<0.02$). Duration of CPR was independent risk factor for mortality. In the United States, Johnson et al⁴² reported 26 cases who received ECMO (and reperfusion when indicated) over a 7-year period, of whom 11 (42%) presented with VF/VT. Of 15 patients with OHCA, 1 patient (6.6%) who presented with VF/VT survived to discharge and made a full neurologic recovery. Survival to discharge was 27.3% (3/11) for IHCA.

Inconsistent results were found in studies comparing extracorporeal CPR vs conventional CPR in OHCA. In South Korea, Kim et al³⁹ found similar rates of survival to hospital discharge in OHCA patients with prolonged conventional cardiopulmonary resuscitation (CCPR) compared with patients who received extracorporeal cardiopulmonary resuscitation (ECPR) (19.4% [86/444] vs 16.4 [9/55]). However, propensity score matching of patients with ≥ 21 minutes of CPR duration showed neurological outcome at 3 months to be more favorable with ECPR than with CCPR (14.5 vs 8.1%). Maekawa et al³⁸ analyzed data from 162 adult Japanese patients with witnessed OHCA of cardiac origin who had undergone cardiopulmonary resuscitation for longer than 20 minutes. Survival to discharge was 32.1% (17/53) with ECPR and 6.4% (7/109) with conventional CPR. Matched propensity analysis showed significantly higher neurologically intact survival at 3 months with ECPR vs conventional CPR (29.2% vs 8.3%; $p=0.018$). In the SAVE-J trial, a prospective observational study of OHCA patients with VF/VT performed in Japan over 3 years, Sakamoto et al¹⁷ compared patients admitted to 26 hospitals providing ECPR vs those admitted to 20 hospitals that did not provide ECPR. Per the protocol analysis, overall 1-month survival was 29% (68/234) with ECPR vs 6% (9/159) in the non-ECPR group. Cerebral Performance Category (CPC) scores of 1 or 2 were achieved at 1 month in 13.7% (32/234) of patients who received ECPR vs 1.9% (3/159) of those without ECPR ($p<0.0001$), and at 6 months in 12.4% (29/234) vs 3.1% (5/159) ($p=0.002$). In Austria, Schober et al⁴³ found that survival to discharge in good neurological condition was 14% (1/11) with ECPR and 6% (13/232) with conventional CPR.

Several studies compared patients with refractory VF/VT vs those with nonshockable rhythms. Leick et al⁴⁴ found 30-day survival was 37.5% (3/8) in patients presenting with VF/VT, and 35% (6/17) in patients

presenting with nonshockable rhythms. The door-to-ECLS implantation time was the only significant and independent predictor of 30-day mortality. In Denmark, [Fjølner et al](#)²⁴ found that of 21 patients adult patients admitted with witnessed, refractory, normothermic OHCA treated with ECPR, 7 (33%) survived to hospital discharge, all with a CPC score of 1 or 2. Survival to hospital discharge was 55.6% (5/9) in patients with VF/VT as the initial rhythm and 16.7% (2/12) in patients presenting with pulseless electric activity or asystole. In patients with refractory OHCA who received ECPR In Lyon, France, [Pozzi et al](#)¹⁸ found survival to discharge was 31.5% (6/19) for VF/VT and 0% (0/49) for nonshockable rhythms (p=0.00). In patients who received ECMO for refractory OHCA in South Korea, [Lee et al](#)²⁵ found 30-day survival of 40% (8/20) for patients with VF/VT, and 67% (2/3) for patients with nonshockable rhythms. In a study in Paris by [Lamhaut et al](#),⁴⁵ although overall survival in patients with refractory OHCA and ECPR was 13.5% (21/156), early field application of ECMO within 60 minutes from a 911 call and careful selection of patients improved survival from 8% to 29%. Absence of coronary angiography was the strongest predictor of mortality (OR 7.1), and only patients presenting with VF/VT were among the survivors.

In 62 consecutive adult patients treated with the Minnesota Refractory VF/VT clinical Protocol (described in detail below), [[name] et al](#)¹¹ reported 45% (28/62) patients were discharged alive and 42% (26/62) were discharged from the hospital with favorable neurological function (CPC 1 or 2).

Clinical Equipoise for a Randomized Trial. [Kim et al](#)⁴⁶ performed a meta-analysis of studies published through 2015 and concluded that, although rates of survival and good neurologic outcome at 3-6 months after cardiac arrest tended to be higher with ECPR than with conventional CPR in overall analyses, the effects of ECPR were not clear in patients with OHCA. According to the [2015 American Heart Association guidelines](#),³¹ “there is insufficient evidence to recommend the routine use of ECPR for patients with cardiac arrest.” In studies published since 2015, survival ranged from 8.8% to 43.5% for ECPR in patients with OHCA (**Table 1**),^{11, 18, 24, 25, 43, 45} and up to 55.6% in patients with VF/VT OHCA.²⁴ Although these results are encouraging, most reports were retrospective, and all studies were observational, with inherent selection bias that no statistical adjustment can eliminate completely. No randomized clinical trials have been performed. Wide variation in results stem from heterogeneous study populations, varying bystander intervention, differences in pre-hospital EMS organizations, the lack of a standardized protocol for ECPR with ECMO in refractory cardiac arrest, differences in in-hospital care, and differences in outcome criteria have resulted in widely varying findings in published study results.

Refractory VF/VT is a spectrum of timing of return of spontaneous circulation (pulses) in response to standard ACLS treatment ranging from return of pulses shortly after the third failed shock (as defined in this protocol) to never. In any individual case, it is impossible to determine where along this continuum the patient may ultimately fall. For patients who will never obtain a pulse, science supports the contention that the sooner ECMO is initiated the potentially better the outcome.^{11, 37, 40, 41, 44, 59, 60} In order to achieve early administration of ECMO from OHCA, it is necessary to begin mobilization from the scene to the hospital immediately following the third failed shock.³⁹ At the same time, for those patients who obtain a pulse in response to standard ACLS treatment later along this continuum may avoid the need for ECMO and it’s attendant complications and cost. Early administration of ECMO precludes

knowing who may have obtained pulses with continued standard ACLS treatment without the need for ECMO intervention. Studies to date^{10, 24, 42, 43} and experience with the Minnesota Resuscitation Consortium Refractory VF/VT protocol^{11, 59, 60} indicate there is potential benefit for initiation of ECMO following out-of-hospital cardiac arrest of up to 90 minutes from 911 call.

Given this state of our collective understanding, clinical equipoise exists. Only a randomized clinical trial can show whether and to what extent early routine ECPR deployment can improve survival in patients with refractory VF/VT OHCA. The proposed ARREST trial at the University of Minnesota will randomize patients with refractory VF/VT OHCA to receive either 1) **Early ECMO Facilitated Resuscitation Arm**, or 2) **Standard ACLS Resuscitation Arm** to provide cardiorespiratory support. Both groups will receive angiography, and PCI when necessary.

Contribution to Public Health In view of the current low survival rates in OHCA, the knowledge gained from the proposed ARREST trial will make an important contribution to our ability to avoid a substantial number of deaths, with significant potential impact on national public health by returning neurologically intact patients to their communities. In the past, very few hospitals had access to emergent ECMO. However, according to the Extracorporeal Life Support Organization registry,³⁶ the number of patients receiving ECPR has increased exponentially in the past 10 years, and the use of ECPR in refractory cardiac arrest represents the most rapidly growing segment.⁴⁷ The ARREST trial will not only generate safety/effectiveness data but also shed light on the comparative costs associated with ECPR, thus providing an informed basis to justify broader implementation and a definitive Phase III clinical trial.

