contribution and relative cost of routine, **early ECMO facilitated resuscitation** to the management and survival of this population need to be assessed in a randomized trial.

ARREST Trial hypothesis. Based on our preliminary results, we hypothesize that routine **early ECMO facilitated resuscitation** will expedite circulatory support, mitigate metabolic derangement, facilitate the identification and treatment of reversible CAD and significantly improve survival to hospital discharge compared with ED-based **standard ACLS resuscitation**.

ARREST Trial. We propose a Phase II, single center, partially blinded, intention to treat, safety and efficacy clinical trial to assess the results of routine **early ECMO facilitated resuscitation** compared with ED-based **standard ACLS resuscitation**. Both strategies represent current standards of care **in our community**. The Minnesota Resuscitation Consortium (MRC) has the patient population, experience, expertise, and infrastructure to successfully execute the proposed study. Two EMS systems currently transport patients to an ED for the **standard ACLS resuscitation**, and three EMS systems transport patients to the University of Minnesota for the routine **early ECMO facilitated resuscitation**.

Specific Aim. The primary objective is to assess the rates of survival to hospital discharge in adult patients (aged 18-75 years) with refractory VF/VT OHCA who are transported to the University of Minnesota and randomized to treatment under the **early ECMO facilitated resuscitation** arm compared with those treated under the **standard ACLS resuscitation**.

Primary Study Endpoint Survival to hospital discharge.

Secondary Endpoints Secondary efficacy endpoints include survival to hospital discharge with mRS \leq 3, 3- and 6-month survival overall and with mRS \leq 3, functional status at discharge, 3 and 6 months (mRS and Cerebral Performance Category [CPC] score), cost per patient and cost per life saved (individual patient billings). Safety endpoints include incidence of serious adverse events (overall due to cardiac arrest and prolonged resuscitation and related to advanced perfusion strategies).

Significance. If our study results indicate potential safety and efficacy, it will provide the basis for a future multicenter clinical trial to assess definitive survival benefit and generalizability of this approach.

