5.4 STRATEGIES FOR RECRUITMENT AND RETENTION

Enrollment is based on patients with refractory VF/VT out-of-hospital cardiac arrest treated by the EMS systems participating in the ongoing MRC Refractory VF/VT Protocol and transported to the University of Minnesota Medical Center, Fairview, where, immediately following hospital arrival, they will be evaluated by the research team for study inclusion and exclusion criteria and, if eligible, randomized and entered in the study.

Because the ARREST Trial will remain transparent to EMS providers, all patients receive the same CPR quality and treatment by the same EMS systems using ACLS guidelines and automated CPR (LUCAS™2), thus limiting potential confounders of differences in resuscitation care and CPR performance. Resuscitation interventions will be performed consistent with local practice and American Heart Association standards.³¹ If the patient has an initial cardiac arrest rhythm of VF/VT and continues to have VF/VT, antiarrhythmics may be administered per standard policy and procedure. If the patient does not develop ROSC after the first 3 defibrillation attempts and meets criteria for the University of Minnesota Refractory VF/VT Protocol (identical to the inclusion criteria for the ARREST Trial, but limited ARREST Trial exclusion criteria), paramedics call a central telephone number/dispatch per their standard practice. The research team will use the standard EMS call to mobilize and be present at the ED for the patient's arrival. MRC Refractory VF/VT Protocol patients are placed on LUCAS and are transferred to the University of Minnesota Medical Center, Fairview Hospital, with ongoing mechanical CPR per standard of care. Immediately following hospital arrival, the research team will evaluate the ARREST Trial inclusion and exclusion criteria and, if eligible, randomize and enter the patient in the study. Thus, paramedics are blinded to the study and out-of-hospital care is implemented using standard ACLS guidelines and automated CPR (LUCAS™2) for both groups.

The clinical CCL/ECMO team is always activated by the initial call and if not already in the hospital, it has a response time of 20 minutes from notification that happens at the time of EMS notification.

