6.2.2 PRODUCT STORAGE AND STABILITY

At all times one device will be pre-primed and placed in the CCL to be available for use. The University of Minnesota initiates ~200 ECMOs per year for resuscitation and other indications and the average time from pre-priming to use is 2-3 days.

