The gross, billing charges per patient will be collected utilizing UB04 data for research purposes. The costs in each group will be averaged. Charges collected will include care in the emergency department (ED), CCL and inpatient care. The costs will be compared between groups and presented both as cost per patient and cost per patient per life saved.

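### The cost endpoints are motivated by the resource burden of early ECMO but measure gross billed charges for the index stay, with no conversion to cost

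*Combined protocol and SAP*

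**What the plan says.** **The question.** Section 2.2 gives the reason for studying cost: "emergent ECMO initiation at short notice with field activation carries significant human and infrastructural costs". It concludes that, ahead of major infrastructure spending, "the relative cost of such a strategy need to be assessed in a randomized clinical trial", together with the contribution of early ECMO to survival. Section 2.1 argues the same way. Section 3 justifies the cost endpoints by the expense of these programmes and their heavy use of staff and resources. The public-health paragraph of 2.2 says the trial will "shed light on the comparative costs associated with ECPR, thus providing an informed basis to justify broader implementation", and it names a Phase III trial in the same sentence.

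**The measure.** Section 8.1 states: "The gross, billing charges per patient will be collected utilizing UB04 data for research purposes". The charges cover ED, CCL and inpatient care. They are averaged by group, called costs, and presented per patient and per life saved. The schedule in 1.3 has one UB-04 entry, at hospital discharge, and none at 3 or 6 months. Sections 3, 9.1 and 9.4.3 say that the cost endpoints are based on billing charges. No section plans a charge-to-cost conversion, resource-use costing or any programme-level cost.

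**Readiness.** Section 5.4 says "The clinical CCL/ECMO team is always activated by the initial call". Section 6.2.2 says "At all times one device will be pre-primed and placed in the CCL to be available for use". Section 6.2.3 describes daily perfusionist rounds to check the devices. None of these is named among the charges to be collected.

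**The concern.** The plan asks what the strategy consumes and then measures what the hospital bills. These are different quantities. A gross charge is a billed price, and its relation to the cost of the resources used can differ between departments. An average charge reported as cost per life saved invites readers to treat it as the resource cost of an additional survivor.

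The comparison between arms is also exposed. The arms may use ED, CCL and ICU care in different proportions. If the charge-to-cost ratio differs across those departments, the ratio of average charges between arms is not the ratio of average costs.

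The readiness that a new site would have to fund (a team on call, a primed circuit) is not separately measured. At stake is how far the published cost figures can support the implementation argument in 2.1 and 2.2. The primary endpoint, stopping rule and safety monitoring are not touched.

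**Working it through.** The documents state no charge, cost, programme budget or cost-to-charge ratio, so there is no cost figure to reproduce. The check compares the question with the measure and then shows how the gap behaves under stated assumptions.

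**Step 1. Question against measure.**
- Question (2.1, 2.2, 3): the relative cost of a strategy that is intensive in staff, resources and infrastructure.
- Measure (1.3, 3, 8.1, 9.4.3): gross UB-04 charges, entered once at discharge, for ED, CCL and inpatient care.
- Link between them: none is specified.

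**Step 2. One charge-to-cost ratio k in every department.** Charge = k × cost in both arms. Cost per patient and per additional survivor are then overstated k-fold, while the early-to-standard ratio is unchanged because k cancels. An assumed k of 2 to 4 gives a 2- to 4-fold overstatement, which only restates the assumption.

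**Step 3. Ratios that differ by department.** Assume 3 in the ED and 4 in CCL/ICU. Let w be the share of the standard arm's true cost that arises in CCL/ICU, and suppose all early-arm cost arises there.
- Early-arm charge = 4 × cost.
- Standard-arm charge = [3(1 − w) + 4w] × cost = (3 + w) × cost.
- Observed ratio ÷ true ratio = 4 / (3 + w).

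| w | 4 / (3 + w) |
|---|---|
| 0 | 4/3 = 1.33 |
| 0.50 | 4/3.5 = 1.14 |
| 0.75 | 4/3.75 = 1.07 |
| 1 | 4/4 = 1.00 |

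Any ED cost in the early arm lowers these values, because the numerator then falls below 4. The documents give neither w nor the ratios. The direction would reverse if the ED had the higher ratio.

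**Step 4. Readiness cost.** Let R be a readiness cost per patient that is not in the charges, and read cost per life saved as the between-arm cost difference divided by the survival difference (the plan gives no formula).
- If R is incurred in both arms: (C_E + R) − (C_S + R) = C_E − C_S. It drops out, so the comparison cannot isolate it.
- If R is incurred only in the early arm: the planned benefit in 9.1 and 9.2 is 0.37 − 0.12 = 0.25, or 1/0.25 = 4 patients per additional survivor. R then adds 4R per additional survivor.

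Which case applies is unclear. Section 5.4 and the screening text of 6.1.1 have the team activated on the EMS call, before randomization. The arm descriptions in 6.1.1 tie mobilization to provisional early-ECMO allocation in one arm and to ROSC in the other. These passages must be reconciled.

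**The case against.** **The measure is disclosed.** The endpoint lists say that the figures are based on billing charges, and 8.1 says gross charges. This stands: nothing is concealed, and renaming alone would add little. It does not supply the missing link between charges and resource cost.

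**This is a secondary endpoint in a Phase II trial, and the stated aim is modest.** This also stands. Section 2.2 asks for relative cost, and nowhere do 2.1 or 2.2 say that the trial will itself cost the infrastructure. The point is therefore an inexpensive improvement, not a flaw in the main inference.

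**Three stronger readings are tempting, and the documents do not support them.**

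- *That standby cost is wholly missing from the bills.* No section says what overhead the charges carry. What can be said is that readiness is not separately measured.
- *That the omission can be priced.* Section 2.1 reports 152 patients in 2.5 years, or 60.8 a year. At a 25-point benefit that is 60.8 × 0.25 = 15.2 additional survivors a year, so an assumed $1 million of annual standing cost would be $1,000,000/15.2, about $66,000 per additional survivor. But 6.2.2 reports about 200 ECMO initiations a year for all indications. Spread over those, the same sum is $5,000 per use, or $5,000/0.25 = $20,000 per additional survivor. The $1 million is itself invented, and the answer turns on an allocation rule that the documents do not give.
- *That the between-arm ratio is overstated by one third.* This needs standard-arm cost to be entirely ED and early-arm cost entirely CCL/ICU. Sections 2.3.1, 3 and 6.1.1 send standard-arm patients with ROSC to the CCL, where they may receive ECMO. Sections 4.1 and 6.1.1 allow early-arm patients to be held in the ED.

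**Conclusion.** The point holds as a mismatch between the cost question and its measure. The planned figures are average billed charges for the index stay. They are not resource costs, and the between-arm ratio can be distorted if charge-to-cost ratios vary by department. The size is unknown from the documents. The range of 1.07 to 1.33 rests on assumed ratios of 3 and 4, an early arm costed wholly in CCL/ICU, and a standard-arm CCL/ICU share between three quarters and none; it shows sensitivity and is not an estimate.

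Readiness cost is not separately measured, and if the team is activated on every call the randomized comparison cannot isolate it. A reader might infer that the trial must therefore add a programme cost to the early arm. The documents do not support that as a correction: ECMO capacity is shared, the activation text conflicts, and the charges may already carry some overhead. The supportable conclusion is that the cost figures, as planned, do not by themselves answer the infrastructure question raised in 2.1 and 2.2.

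**What to change.** In sections 3, 8.1 and 9.4.3:

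1. Convert UB-04 charges to estimated cost, department by department, using the hospital's own cost-to-charge ratios, and name their source and year.
2. Report cost per patient and cost per additional survivor from the converted figures. Show raw charges alongside, labelled *billed charges, index stay*.
3. State that programme readiness cost (team standby, primed circuit, device checks) is not separately measured, so the figures do not by themselves settle the infrastructure question in 2.1 and 2.2.
4. Reconcile the team-activation statements in 5.4 and 6.1.1, so that readers know whether activation is common to both arms.

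A programme-cost scenario is optional. It would need an explicit rule for allocating shared ECMO capacity and a check that overhead in the converted costs is not counted twice.

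The cost is protocol wording and a request to hospital finance for the ratios, plus departmental detail if the UB-04 extract lacks it. No new patient procedure is needed, and sample size and the primary analysis do not change. The downside is that ratio-based costs are approximate.
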